## **Amendment 2 to the Statistical Analyses Plan**

**Evaluation after 6 years**

**CVD risk scores, CVD risk factors, and ultrasound data**

**2024-01-12**

## **VIPVIZA Amendment 2 to the Statistical Analyses Plan**

The present amendment to the VIPVIZA statistical analysis plan includes details on planned analyses of the VIPVIZA intervention after 6-year follow-up, to be presented in two publications: one evaluating the CVD risk (study A) and one evaluating cIMT and atherosclerotic plaque progression (study B). For the analysis of the 6-year follow-up of VIPVIZA, the description of outcome variables and study populations of the original VIPVIZA statistical plan is still valid, unless otherwise noted in this amendment.

The 3-year follow-up examinations were performed from September 5 2016 to May 28 2019 and all participants from both groups, as well as their respective family physicians in primary care, received the pictorial and written result of the ultrasound examination. Thus, directly after the VIPVIZA 3-year follow-up, all participants in the initial control group (IC) underwent the intervention for the first time and the initial intervention group (II) underwent a second (repeated) intervention. This means that the arms of the trials are no longer parallel and that studies following the progression of the groups after the 3-year follow-up will be post-trial evaluations that no longer allow for estimation of the VIPVIZA intervention effect through direct comparisons of IC and II. Even so, it is still of interest to evaluate the long-term development of the two arms, and to investigate if there still exist group differences in CVD risk and severity of atherosclerosis, e.g. due to the different lag times from when the intervention was given. Furthermore, there are few studies about the development over time of riskfactors and atherosclerosis (assessed by imaging, ultrasonography). Therefore, we will investigate development (regression-progression) of risk factors for CVD and atherosclerosis as assessed by carotid ultrasonography in the complete study population and subdivided in combinations of subgroups, and in particular on age groups (40-, 50- and 60 year old), sex, educational level, severity of ultrasound result. We will also separately analyze scenarios with worst vs best development (e.g. groups of individuals with severe progression vs groups with regression).

The VIPVIZA 6-year collection of data on cardiovascular risk factors, health behaviors and other questionnaires were conducted between December 1st 2019 and March 17th 2023, and the carotid ultrasound examinations were performed between January 13th 2020 and May 13th 2023.

### **Study A: Evaluation of cardiovascular risk, single risk factors and health behaviors at 6-year follow-up examination at the 6-year follow up examination of VIPVIZA**

Research question:

- What is the development of cardiovascular risk and cardiovascular risk factors within the VIPVIZA treatment arms up to the 6-years follow-up?
- Is there a difference in cardiovascular risk and cardiovascular risk factors between the treatment arms at the 6-year follow up?

*Data and variables:* The analysis will utilize the VIPVIZA panel data, which consists of the baseline, 1-year, 3-year and 6-year follow-up measurements. During the period between 3-year and 6 follow-up of VIPVIZA, SCORE2 was introduced in the ESC guidelines(1). SCORE2 will replace SCORE as, along with Framingham risk score (FRS), one of two primary outcomes in the 6-year follow-up study of study A. Secondary outcomes are systolic and diastolic blood pressure, serum triglycerides, LDL cholesterol, HDL cholesterol, waist circumference and current smoking.

*Analyses:*

We will graphically visualize mean trajectories of outcomes, measured from baseline over 1-year, 3-year and 6-year of follow-up for the two arms and when stratifying the two arms by baseline age groups. Development of continuous outcomes will be analyzed using mixed effects repeated measures with group (II or IC), time point (baseline, 1, 3 or 6 years) and group\*times interaction as fixed factors, assuming an unstructured covariance matrix. Corresponding analysis of smoking will be performed using a generalized linear mixed effects model with a logistic link function, with group, time points and group\*time point as fixed effects and a random effect for participant.

As group differences at 1 and 3 years of are already published on all outcomes except SCORE2(2,3), only group differences in outcomes at 6 years will be statistically tested and presented with 95% confidence intervals. They will be estimated using ANCOVA for continuous outcomes, adjusted for corresponding baseline value. Serum triglycerides will be transformed using the natural logarithm before analysis, and group differences on logarithmic scale will be re-transformed back to a ratio of geometric means in the original scale.

Prevalence ratio of smoking will be estimated from Poisson regression with robust Huber-White sandwich estimator of standard errors, adjusting for baseline smoking status. All ANCOVA/Poisson models will be fitted with and without adjustments for sex and educational level.

For SCORE2, group differences at 1-years and 3 years will be estimated using previously described ANCOVA model.

In addition, we will conduct stratified analyses by:

- Sex/Gender (men/women)
- Age-groups at baseline (40, 50 or 60 years).
- Baseline educational level
- Risk level at baseline
- Severity of ultrasound result

The main analysis will be performed on complete case data. Analyses using multiple imputation of missing data will be performed as secondary analyses. No correction for multiple comparisons to control the familywise error rate will be performed. This is motivated

by the fact that this is a post evaluation of the original trial and does not fall under the convention of adjusting for multiplicity within randomized trials.

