10.2 Selection criteria

10.2.1 Inclusion criteria were based on 1/ the aim of targeting subjects at intermediate risk of CVD, and 2/established clinical criteria (smoking, diabetes, hypertension, abdominal obesity) or evaluation of levels and distribution of clinical CVD risk markers (S-LDL) in the 2011 VIP population. In this population, the cut-off for the 4th quartile among 50 years old men and women was 4.4 mmol/L and 4.0 mmol/L, respectively, while 9% and 12% respectively had S-LDL concentrations \leq 2.5 mmol/L, and 81% and 88% respectively had S-LDL concentrations \leq 4.5 mmol/L.

- age=40 and a history of CVD at age <60 years among first-degree relative(s)
- age=50 years and at least one of the following: a history of CVD at age <60 years among first-degree relative(s), smoking, diabetes, hypertension, S-LDL-cholesterol \geq 4.5 mmol/L, abdominal obesity defined by waist >88cm for women and >102 cm for men
- age=60 years

Individuals are included in the study only once, at whichever qualifying age point is achieved first.

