13.2.3 Summary of planned analyses

The differences in primary outcomes (SCORE risk and Framingham Risk Score) at one year between the treatment groups will be measured and analysed using t-test, for a detailed statistical analyses plan see Appendix 4. As the group sizes are large (more than thousand), it is valid to assume normal distribution of the error around the mean value estimates in both the intervention and the control group. A two-sided p-value <0.05 will be regarded as statistically significant. Complementary to the absolute difference in the Score and the statistical testing of hypotheses, Cohen's effect size will be derived for the difference in mean outcome values divided by a pooled standard deviation of the Score between the 2 groups.

In sensitivity analyses, we will conduct a linear regression covariate-adjusted analysis. We will use the continuous form of the primary outcomes (SCORE risk and Framingham Risk Score) as outcome in the

regression analysis. We will assess the effects of the intervention independently for each of the outcome measures. As many of the baseline co-variates (including sex and age) are related to the prognosis of outcomes, adjustment of pre-defined covariates in the regression analysis might yield in adjusted coefficients which are slightly further from 1.

We will also analyze the changes of SCORE and FRS from baseline to 1-year follow-up and use regression methods to identify predictors of the changes in the scores.

Since patients are recruited into the study during three years from mid-2013 to mid-2016, any change in physicians' prescribing behaviour over the course of the study will be evaluated by comparing prescriptions issued for lipid-lowering and anti-hypertensive medication to participants recruited during the first, second and third years.

Similar statistical methods will be applied for evaluation of the three-year results. At that time point also changes in plaque distributions and IMT variables including differences between intervention and control group will be evaluated.

In long-term, adding risk communication using visualisation of carotid ultrasound results will be compared to routine CVD risk assessment and control within the primary health care setting in hospitalisation due to stroke, myocardial infarctions and revascularisations (at 5-year and 10-year) and reducing overall mortality and cause-specific mortality due to myocardial infarctions and stroke (at 5-year and 10-year) compared to.

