## **B. Evaluation of subclinical atherosclerosis measured by carotid ultrasound at the 6-year follow-up of VIPVIZ, including IMT, carotid plaque prevalence and carotid plaque characteristics.**

*Research questions:*

- What is the development of subclinical atherosclerosis measured by carotid ultrasound within the VIPVIZA treatment arms up to the 6-year follow-up?
- Is there a difference in the degree of subclinical atherosclerosis measured by carotid ultrasound between the treatment arms at the 6-year follow-up?

*Data and variables:* The primary outcomes are carotid IMT and carotid plaque prevalence (categorized as no plaque, unilateral plaque, and bilateral plaque), and carotid plaque area ( $\text{mm}^2$ ).

Secondary outcomes are carotid plaque greyscale median (GSM) and carotid plaque thickness (mm)

*Analyses:*

We will graphically visualize trajectories of mean values and prevalence of outcomes, measured from baseline over 3-year and 6-year of follow-up for the two arms and when stratifying the two arms by baseline age groups.

Development of continuous outcomes (carotid IMT and plaque area) will be analyzed using mixed effects repeated measures with group (II or IC), time point (baseline, 3 or 6 years) and group\*times interaction as fixed factors, assuming an unstructured covariance matrix.

Corresponding analysis of plaque prevalence (one and two-sided, respectively) will be performed using a generalized linear mixed effects model with the fixed effects and a random effect for participant. As group differences at 1 and 3 years are already published(4), only group differences in outcomes at 6 years will be presented. For continuous outcomes, they will be estimated using ANCOVA, adjusted for corresponding baseline value. Group difference of plaque prevalence at 6-years will be evaluated using an ordinal proportional odds model. All ANCOVA/proportional odds models will be fitted with and without adjustments for sex and educational level.

We will also conduct stratified analyses and evaluate intervention effects by

- Sex/Gender (men/women)
- Age-groups at baseline (40, 50 or 60 years).
- Severity of ultrasound result
- Baseline educational level

The main analysis will be performed on complete case data. Analyses using multiple imputation of missing data will be performed as secondary analyses. No correction for multiple comparisons to control the familywise error rate will be performed.

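### The 6-year ANCOVA models for continuous outcomes leave baseline age group (40/50/60) out of the covariate set, which gives up a small amount of precision at no saving

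*SAP*

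**What the plan says.** In SAP Amendment 2, Study A, the 6-year group differences are specified thus: "They will be estimated using ANCOVA for continuous outcomes, adjusted for corresponding baseline value". Smoking is analysed by Poisson regression, "adjusting for baseline smoking status". The further covariates are given in one sentence: "All ANCOVA/Poisson models will be fitted with and without adjustments for sex and educational level".

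Study B follows the same pattern. Its continuous outcomes use ANCOVA with the baseline value. For plaque, "Group difference of plaque prevalence at 6-years will be evaluated using an ordinal proportional odds model", with no baseline plaque term stated. Then: "All ANCOVA/proportional odds models will be fitted with and without adjustments for sex and educational level".

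Age group appears at 6 years only in the trajectory plots and in the list of stratified analyses, in both studies. It is not a covariate in any of the three model types. Neither study says whether the fit with or without covariates is the main one.

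Protocol 10.2 ties eligibility to age: entry at 40 requires premature CVD in a first-degree relative, entry at 50 requires at least one listed risk factor, and entry at 60 has no further criterion. Protocol 13.2.3, when planning adjusted sensitivity analyses, gives this reason: "As many of the baseline co-variates (including sex and age) are related to the prognosis of outcomes".

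**The concern.** The Protocol names sex and age together as prognostic. The SAP keeps sex, adds education and drops age without giving a reason. The cohort is three groups ten years apart with different entry rules, so age group also carries information on how participants were selected.

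The baseline value of the outcome does not absorb all of this. A single IMT or blood pressure reading contains measurement error, and age then says something more about the participant's true level. In ANCOVA, a prognostic covariate left out stays in the residual variance and widens the interval for the group difference.

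Two features add to the case. Protocol 12.1 describes a simple randomisation list with no stratification, so age balance is left to chance. The main 6-year analysis uses complete cases, so balance among those who return also depends on attrition. Stratified analyses do not address either, because they give separate estimates and no age-adjusted overall contrast.

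At stake is a small loss of efficiency, most relevant to IMT, a primary outcome of Study B and the variable that set the sample size in Protocol 13.1.

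**Working it through.** **1. The plan's own figures.** The documents give no power or precision figure for the 6-year analysis. The nearest is the table in Protocol 13.1: two-sided alpha 0.05, power 0.80, 1500 per group. The minimum detectable change (MDC) is SD × (1.960 + 0.842) × √(2/n).
- SCORE: 1.40 × 2.802 × √(2/1500) = 0.143. The table says 0.143, so it reproduces.
- CIMT: 0.2 × 2.802 × √(2/1500) = 0.0205. The table says 0.02, which agrees after rounding.

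**2. Inputs for IMT.**
- From Protocol 13.1: SD 0.2 mm, so total variance 0.04; progression rates 0.010 and 0.0147 mm/year.
- Assumed, not in the documents: the progression rate serves as the between-person age gradient; age mix 15/35/50% at 40/50/60; reliability ρ of one baseline reading 0.6-0.9; variance of individual 6-year change 0.003 mm².

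**3. Formulas.** The age mix gives a mean of 53.5 years and a variance of 0.15 × 13.5² + 0.35 × 3.5² + 0.50 × 6.5² = 52.75. The variance due to age is A = rate² × 52.75, that is 0.00528 (13% of 0.04) at 0.010 and 0.01140 (28%) at 0.0147.
- Residual variance given baseline only: R0 = 0.043 − (0.04ρ)²/0.04
- Residual variance given baseline and age: R1 = 0.043 − A − (0.04ρ − A)²/(0.04 − A)
- Reduction in residual variance: 1 − R1/R0
- Narrowing of the interval: 1 − √(R1/R0)

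**4. Worked case, 0.0147 mm/year, ρ = 0.7.** R0 = 0.043 − 0.0196 = 0.02340. R1 = 0.03160 − 0.01660²/0.02860 = 0.02197. The reduction is 6.1% and the interval is 3.1% narrower.

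**5. Range.**

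| Gradient (mm/year) | ρ | R0 | R1 | Variance reduction | Interval narrower by |
|---|---|---|---|---|---|
| 0.010 | 0.9 | 0.01060 | 0.01054 | 0.6% | 0.3% |
| 0.010 | 0.8 | 0.01740 | 0.01716 | 1.4% | 0.7% |
| 0.010 | 0.7 | 0.02340 | 0.02285 | 2.3% | 1.2% |
| 0.0147 | 0.8 | 0.01740 | 0.01676 | 3.7% | 1.9% |
| 0.0147 | 0.7 | 0.02340 | 0.02197 | 6.1% | 3.1% |
| 0.0147 | 0.6 | 0.02860 | 0.02605 | 8.9% | 4.6% |

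Per 3000 analysed (an illustrative number, since no 6-year n is given), the cases at ρ = 0.7-0.8 are worth about 40-70 participants at 0.010 mm/year and about 115-195 at 0.0147. With an age mix of 10/30/60% the full range of variance reduction is 0.5-7.2%; with equal thirds it is 0.8-12.6%.

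**6. Risk scores.** A simulation of a multiplicative, age-driven score (assumed log-score slope 0.05-0.10 per year, baseline to 6-year correlation of the non-age part 0.5-0.85) gave a partial R² for age beyond the terms already in the model of about 0.01-0.15. A partial R² of 0.05 lowers the SE by 2.5% and takes the SCORE MDC from 0.143 to 0.140.

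**7. The other two models**, by simulation with an assumed 2400 analysed.
- Poisson for smoking: SE of the log prevalence ratio 0.0974 without age and 0.0976 with it. No gain.
- Proportional odds for plaque, assumed odds ratio (OR) of 2.5 per ten years of age: SE 0.0774 without age and 0.0788 with it. The log odds ratio moves from −0.205 to −0.217 and mean |z| from 2.65 to 2.76. At an OR of 1.8 mean |z| does not rise. These runs had 25 replicates per setting and are indicative only.

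**The case against.** The strongest case against is that this hardly matters. Continuous outcomes are already adjusted for their baseline value, which carries much of the age information. The likely gain for IMT is an interval 1-3% narrower, on a contrast that the SAP itself describes as post-trial and no longer an estimate of the intervention effect, because controls received their results after 3 years. Most inputs are assumed: published within-person progression rates stand in for a between-person age gradient, and age mix, reliability, slope variance and 6-year sample size are not in the documents. Age is not ignored either, since age-stratified results are planned. All of this stands, and it limits the point to a cheap improvement.

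A reader might infer more: that every 6-year interval is wider than it need be, with the largest losses for IMT and plaque. The documents and the check do not support that. Smoking gains nothing. In the proportional-odds model, adding age moves the conditional odds ratio away from 1 without shrinking its SE, so the intervals on the log-odds scale do not narrow.

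A reader might also infer bias. Leaving a baseline covariate out of a randomised comparison does not by itself bias it.

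Finally, 6-year data collection ended in May 2023 and the amendment is dated January 2024, so the data are already in hand. A change to the main model should therefore be dated and made without sight of the group comparisons.

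**Conclusion.** The point holds for the continuous outcomes and is small. Age group is available for everyone, determines eligibility and is called prognostic by the Protocol, yet it is missing from the 6-year covariate set. For IMT the residual variance given up is about 0.6-8.9% across the assumed range and most plausibly 1-6%, or intervals about 1-3% wider than necessary. The direction is firm; the size depends on the assumptions listed and cannot be derived from the documents.

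The unnamed main model is a secondary matter. Each outcome has two estimates, with and without covariates, and nothing fixes which will be the headline. The missing baseline plaque term in the proportional-odds model is a separate gap of at least similar weight to the missing age term there.

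**What to change.** Replace the covariate sentence in Studies A and B with one that:
- adds baseline age group (40/50/60, categorical) to sex and educational level for all continuous outcomes and, for consistency, in the Poisson and proportional-odds models;
- names baseline value + sex + age group + education as the main model for each 6-year contrast;
- keeps the fit without sex, age group and education as a sensitivity analysis.

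The cost is one sentence per study and two degrees of freedom, with no new data. For plaque, the conditional odds ratio changes with the covariate set, so the report should say which covariates it is conditional on. If the 6-year group comparisons have already been run, the age-adjusted fit should be labelled as an added sensitivity analysis and should not replace the main result.

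### The 6-year subgroup analyses compare the arms stratum by stratum with no arm-by-factor interaction, so chance differences between strata can be mistaken for effect modification

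*SAP*

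**What the plan says.** SAP Amendment 2, Study A, Analyses: "In addition, we will conduct stratified analyses by" sex, baseline age group, baseline education, baseline risk level and ultrasound severity.

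Study B, Analyses: "We will also conduct stratified analyses and evaluate intervention effects by" sex, baseline age group, ultrasound severity and baseline education.

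The only interaction in the amendment is group by time point in the repeated-measures models ("interaction as fixed factors, assuming an unstructured covariance matrix"). For Study A, "only group differences in outcomes at 6 years will be statistically tested and presented with 95% confidence intervals". Both studies decline multiplicity correction; Study A's wording is "No correction for multiple comparisons to control the familywise error rate will be performed", justified there by the post-trial setting.

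Three related statements matter:

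- The introduction to the amendment says that comparisons after year 3 "no longer allow for estimation of the VIPVIZA intervention effect through direct comparisons of IC and II".
- The introduction also plans to describe development over time "subdivided in combinations of subgroups", with no limit on how many.
- The entry "Severity of ultrasound result" has no time point in either list, whereas age and education are tied to baseline in both, and risk level in Study A.

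**The concern.** A significant arm difference in one stratum and a non-significant one in another does not show that the two differences differ. That needs a direct comparison of the stratum estimates, which is what an arm-by-factor interaction provides. Without it, the plan produces stratum results that invite a reading such as an effect in women but not in men, and offers no means of checking it. Study B's wording is the language of effect modification.

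Two wording problems affect what the strata mean. If ultrasound severity were taken from the 3- or 6-year scan, the strata would be formed after randomisation and the arms within them need no longer be comparable. In Study B such strata would also condition on the outcome. And Study B's reference to intervention effects contradicts the amendment's own introduction.

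The overall 6-year arm comparisons are unaffected. At stake are the subgroup statements in the two planned publications.

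**Working it through.** **Inputs.** Protocol 13.1 gives two-sided working values of alpha 0.05 and power 0.8, and 1500 per group. SCORE has SD 1.40, minimum detectable change 0.143 and relevant change 0.5. Framingham (FRS) has SD 6.60, minimum detectable change 0.7 and relevant change 1. The number attending at 6 years is not given; 1000 to 1500 per arm is assumed.

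**Reproducing the protocol's figure.** Minimum detectable change = (1.960 + 0.842) × SD × √(2/n).
- SCORE: 2.802 × 1.40 × √(2/1500) = 0.143, as stated.
- FRS: 2.802 × 6.60 × √(2/1500) = 0.675, which the protocol gives as 0.7.

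**Same true difference in every stratum, overall power 80%.** The expected overall z is 2.802. A stratum holding a fraction f of participants has expected z of 2.802 × √f and power Φ(2.802√f − 1.960).
- Halves: Φ(1.981 − 1.960) = 0.508. P(exactly one significant) = 2 × 0.508 × 0.492 = 0.50.
- Thirds: Φ(1.617 − 1.960) = 0.366. P(some but not all significant) = 1 − 0.366³ − 0.634³ = 0.70.

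**At the protocol's relevant changes, 1500 per arm.**
- SCORE 0.5: overall z = 0.5 / (1.40 × √(2/1500)) = 9.78. Power in halves or thirds is about 100%, so a mixed picture has probability about 0%.
- FRS 1: overall z = 1 / (6.60 × √(2/1500)) = 4.149, power 98.6%. Halves: Φ(2.934 − 1.960) = 0.835, mixed 2 × 0.835 × 0.165 = 0.28. Thirds: Φ(2.396 − 1.960) = 0.668, mixed 1 − 0.668³ − 0.332³ = 0.665.

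**At 1000 per arm, FRS 1.** Overall z = 3.388. Halves: Φ(2.396 − 1.960) = 0.668, mixed 0.44. Thirds: Φ(1.956 − 1.960) = 0.498, mixed 0.75. SCORE 0.5 stays near zero (about 1% for thirds).

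**What an interaction test offers.** It holds the false-positive rate for effect modification at 5% per factor and outcome. With two equal strata its standard error is twice that of the main effect (√(8/n) against √(2/n)), so at 1500 per arm the minimum detectable difference between strata is 2 × 0.143 = 0.286 for SCORE and 2 × 0.675 = 1.35 for FRS. An interaction as large as a main effect with 80% power is detected with power Φ(2.802/2 − 1.960) = Φ(−0.559) = 0.29.

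**Multiplicity that remains.** If the tests were independent, the chance of at least one false positive for one outcome would be 1 − 0.95⁵ = 0.23 over Study A's five factors and 1 − 0.95⁴ = 0.19 over Study B's four.

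**The case against.** The plan never says that effect modification will be inferred by comparing p-values across strata. Both studies' research questions ask about development within arms and the arm difference at 6 years, not about who benefits more. This stands: a reader might infer that misleading subgroup claims will follow, but the documents support only that they can.

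The 80% power case is close to the worst case for two strata, because 2p(1 − p) peaks at p = 0.5. This also stands, and is why the results at the relevant changes are shown. Those changes were set for baseline to 1 year, however, before controls received their ultrasound result, so they need not describe year 6.

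A reader might infer that a later scan will define severity. The documents do not show this: both arms are scanned at baseline (protocol 9.2.2 and 12.3), and what controls lack until year 3 is disclosure, not data. Nor would a later scan condition on the outcome in Study A, whose outcomes are risk scores, risk factors and smoking.

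One could also argue from the many stratum tests to a high chance of some false positive. That is a multiplicity point, which Study A addresses with a stated reason and which interaction tests do not remove. The reason given does not, however, turn separate stratum results into a test of difference.

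Finally, the detailed SAP (protocol Appendix 4) was not available and may define subgroup methods. The amendment carries over its outcome variables and study populations, and does not mention subgroup methods.

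**Conclusion.** The concern holds in this form: the 6-year strata are planned without any test of whether the group difference varies between them, so chance differences can be mistaken for effect modification. This is clearest in Study B, whose stated aim for the strata also conflicts with the amendment's introduction. The missing time point for ultrasound severity is an ambiguity to close, not a demonstrated error.

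With an identical true difference in every stratum, a mixed picture arises about 50% (halves) or 70% (thirds) of the time at 80% overall power. At the protocol's relevant changes with 1500 per arm it ranges from about 0% for SCORE to 28% (halves) or about two thirds (thirds) for FRS.

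This assumes equal stratum sizes, the protocol's SDs (none is given for SCORE2) and unadjusted comparisons. Adjusting for baseline would raise precision, but at 95% overall power the mixed picture still occurs 40% (halves) or 74% (thirds) of the time.

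**What to change.** 1. For each factor, fit one model on all participants with arm, factor, arm-by-factor interaction and the baseline value, keeping the planned model type. On ratio scales the interaction is then a ratio of ratios.
2. Report the interaction estimate with its 95% CI as the only basis for any claim that the group difference varies. Show stratum estimates with CIs, labelled exploratory.
3. Define ultrasound severity from the baseline scan in both arms, and state the categories for severity, education and risk level.
4. In Study B, replace the reference to intervention effects with group differences, to agree with the introduction.
5. If Appendix 4 already specifies interaction tests, a cross-reference is enough for items 1 and 2.

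The cost is SAP wording and a few model terms, with no new data. The drawback is low power, about 29% in the case worked above, so the SAP should say that a non-significant interaction is not evidence of a uniform difference. The change does not control multiplicity across factors and outcomes, and the SAP should say that too.

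### The main 6-year group difference for continuous outcomes leaves out the earlier visits of people not seen at year 6; using them is a cheap, modest improvement

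*SAP*

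**What the plan says.** Study A of SAP Amendment 2 sets out a four-visit dataset: "The analysis will utilize the VIPVIZA panel data, which consists of the baseline, 1-year, 3-year and 6-year follow-up measurements". Of the group differences at 1, 3 and 6 years, only the 6-year one is to be tested and given a 95% confidence interval. On method: "They will be estimated using ANCOVA for continuous outcomes, adjusted for corresponding baseline value". Each model is fitted with and without sex and educational level; neither version contains a 1- or 3-year outcome value. SCORE2 has no published 1- and 3-year results, so: "For SCORE2, group differences at 1-years and 3 years will be estimated using previously described ANCOVA model".

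On missing data: "The main analysis will be performed on complete case data", followed by "Analyses using multiple imputation of missing data will be performed as secondary analyses". Amendment 2 names no imputation variables.

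A repeated-measures model with group, time point and their interaction "as fixed factors, assuming an unstructured covariance matrix" is also planned, but for the development of the outcomes over time. Baseline is one of its time points, so each arm has its own baseline mean. The text does not say whether the model uses every observed visit.

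Study B (ultrasound at baseline, 3 and 6 years) follows the same pattern: "For continuous outcomes, they will be estimated using ANCOVA, adjusted for corresponding baseline value", complete cases as main analysis, imputation as secondary.

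**The concern.** An ANCOVA of the 6-year value on arm and baseline needs a 6-year value. Someone measured at baseline, 1 and 3 years and then lost drops out of it entirely, although those measurements are on file and predict the missing value.

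Two things are at stake. One is precision, which is thrown away under any loss pattern. The other is the missing-data assumption: complete-case ANCOVA relies on loss being unrelated to the 6-year outcome once arm and baseline are known, whereas an analysis of all visits also allows loss to depend on the observed 1- and 3-year values.

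The choice also sits awkwardly with the protocol. Section 13.2.1 says that everyone taking part will be analysed, and the summary promises evaluation by intention to treat. The protocol amendment on the 6-year follow-up justifies that visit by the extra certainty of three ultrasound time points over two, yet the main 6-year contrast uses two.

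**Working it through.** **Inputs from the documents.** 3532 participants were included (protocol amendment, section A), with 1:1 allocation, so 1766 per arm. Planning drop-out is 15% (protocol 13.1). The planning SD for FRS is 6.60 and its relevant change 1 point (table in 13.1).

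**Assumed, because the documents do not give them.** 6-year loss of 15-30%; correlations between visits of 0.5-0.82; reasons for loss.

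**The plan's own figures.** Amendment 2 gives no sample size, power or loss for year 6. Protocol 13.1 reproduces adequately: 3000/(1 - 0.15) = 3530 against 3500 stated. The FRS minimum detectable change is 2.80 x 6.60 x sqrt(2/1500) = 0.675 against 0.7.

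**Precision under random loss.** Let m be the share lost at year 6, f the share of those who had earlier follow-up visits, and R the squared partial correlation of the 6-year value with the earlier follow-up values given baseline. The proportional fall in variance is

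R x m x f / (1 - m + m x f), which equals R x m when f = 1.

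| Setting | R | m = 15%, f = 1 | m = 30%, f = 1 | m = 15%, f = 0.5 | m = 30%, f = 0.5 |
|---|---|---|---|---|---|
| Study A, all correlations 0.5 | 0.167 | 2.5% | 5.0% | 1.4% | 2.9% |
| Study A, 0.70-0.82 | 0.407 | 6.1% | 12.2% | 3.3% | 7.2% |
| Study B, all 0.5 | 0.111 | 1.7% | 3.3% | 0.9% | 2.0% |
| Study B, 0.70-0.80 | 0.34 | 5.1% | 10.2% | 2.8% | 6.0% |

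Example: 0.407 x 0.15/0.85 = 7.2%. In practical terms, at correlation 0.7, 15% loss and f = 1, the FRS minimum detectable difference moves from about 0.48 to 0.47.

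**Standard error of complete-case ANCOVA**, in outcome SDs: sqrt(1 - r^2) x sqrt(2/n). With r = 0.7, n = 1766 x 0.85 = 1501 gives 0.026, and n = 1766 x 0.70 = 1236 gives 0.029.

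**Bias if loss depends on the outcome's own 3-year value** (simulation, true difference -0.15 SD, correlations 0.70-0.82; slopes are log-odds of loss per SD, control/intervention):

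| Slopes | Complete-case bias, 15% loss | 30% loss |
|---|---|---|
| 0.6/0.6 | +0.002 | +0.003 |
| 0.3/0 | +0.013 | +0.026 |
| 0.6/0.3 | +0.015 | +0.026 |
| 0.6/0 | +0.027 | +0.052 |

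An all-visit model with equal baseline means stayed within 0.0011 SD throughout. On the FRS planning SD, 0.01-0.05 SD is 0.07-0.33 points.

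**Bias if loss follows the 3-year ultrasound result** (disclosed to both arms; correlation 0.2-0.5 with the score; slopes 0.6/0.3 or 0.6/0; absolute values):

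| Effect of the result on later risk | Complete case | All-visit, score only |
|---|---|---|
| None | 0.003-0.026 | at most 0.001 |
| -0.2 SD per SD, both arms | 0.001-0.024 | 0.008-0.034 |

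Imputation by arm with the ultrasound result in the model stayed within 0.0011 SD.

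**Loss depending on the unseen 6-year value in one arm** (log-odds 0.5 per SD, all correlations 0.7, nominal 15/25/35% loss): complete-case bias 0.041/0.065/0.088 SD, earlier-visit analysis 0.031/0.050/0.067. Both are biased.

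**Why the planned model cannot be used unchanged.** With free baseline means and complete data, its change-from-baseline contrast has 2/(1 + r) times the ANCOVA variance: 1.33 at r = 0.5, 1.18 at 0.7 and 1.11 at 0.8. The gain needs a common baseline mean or baseline as a covariate.

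**The case against.** The strongest reply is that both tools are already planned, so the dispute is only over which analysis is called main. Moreover, Amendment 2 describes the 6-year comparison as a post-trial evaluation that no longer estimates the intervention effect. Both points limit the consequence. They do not remove it: the between-arm question is still posed, tested and given an interval in Study A, and the planned model would lose precision if used as written.

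A second reply is that the proposed main model is not reliably better. This stands. Where loss follows the ultrasound result and that result lowers later risk, the all-visit model of the score alone is no better than complete cases and often worse. That is why imputation must be reported beside it. Nor do the imputation runs prove robustness: they look clean because the variable that generated the loss was in the imputation model.

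Third, the precision gain depends on those lost at year 6 having been seen earlier. Withdrawal, death and migration can remove people before the 1- or 3-year visit. This also stands, hence the lower range.

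Finally, the original statistical plan (protocol Appendix 4) is not among the documents and might list imputation variables. Amendment 2 carries over its outcome variables and study populations, but itself sets the analyses at issue.

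**Conclusion.** The point holds as a recommended, inexpensive improvement of minor to moderate weight. For continuous outcomes, the main 6-year contrast discards earlier visits that a planned model could use. Under random loss and the assumed inputs, the cost is about 2-12% of variance if nearly all those lost had earlier visits, about 1-7% if half did not, and less if fewer did.

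A reader might infer that the complete-case estimate is biased. The documents do not support that: they give no 6-year loss, no reasons for loss and no sign that loss differs by arm. If loss depends on earlier values alike in both arms, bias is near zero. The 0.01-0.05 SD range needs dependence that differs between arms, which is a stress assumption; its upper end needs 30% loss and dependence in one arm only.

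A reader might also infer that an all-visit model always reduces bias. It does so when loss depends on the observed values in the model, not in every case examined here.

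No change of main analysis is claimed for smoking, plaque area or plaque status ("categorized as no plaque, unilateral plaque, and bilateral plaque").

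**What to change.** In Amendment 2:

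- Take the main 6-year contrast for SCORE2, FRS, the other continuous risk factors (triglycerides on the log scale, as planned) and IMT from the repeated-measures model. Fit it to all observed visits, with a common baseline mean or baseline as a covariate.
- Keep complete-case ANCOVA as a sensitivity analysis.
- Specify the multiple imputation: by arm, with earlier values of the outcome and, in Study A, the 3-year ultrasound result. Report it beside the main estimate.
- State how deaths before year 6 are treated, and report 6-year loss and deaths by arm.

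The cost is SAP wording and re-specifying two analyses already planned, with no new data. The downsides are reliance on the covariance or imputation model, the need to impute the ultrasound result for those who missed year 3, and implicit 6-year values for people who died unless this is addressed. Neither analysis corrects for loss that depends on the unseen 6-year value.
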